#### 7.1.11 Fidelity of intervention delivery

The fidelity of delivery of MM and CM will be assessed and its impact on acamprosate adherence and clinical outcomes will be examined. All MM sessions will be audio recorded. A random sample, stratified by pharmacists delivering the intervention, of 10% of all audio recordings of each the MM and MM+CM interventions will be rated by at least 2 trained raters who will be

members of the research team, using a checklist of required elements. The raters will be supervised by the post-doctoral research pharmacist and the trial manager, through regular meetings. The post-doctoral research pharmacist and trial manager will check 10% of the fidelity ratings completed by the raters. The information gained from checking the raters fidelity ratings will be fed back to the raters during the regular supervision meetings to ensure as much accuracy as possible of the fidelity rating. The information from the fidelity checks will be fed back to the pharmacists delivering the MM and CM to improve intervention fidelity.

#### 7.1.12 Success indicators

At the end of the pilot phase descriptive analysis will be undertaken to assess recruitment rates in each of the study sites over the first 3 months. These will be assessed against initial targets of recruiting on average 11 participants per month per site. The criterion for proceeding to the full trial will be achieving a recruitment rate of 55 participants per month across the 5 sites at least during the last month of the pilot phase. A higher recruitment rate has been set for the pilot phase of the trial, which has been calculated based on the average number of patients who complete detoxifications at the 5 trial sites (approximately 291 detoxifications per month across the 5 sites) and the clinical and research experience of the co-applicants. It is anticipated that after an initial lag in recruitment while the trial is being established, recruitment rates will increase. However, this high rate may not be maintained throughout the trial as it is dependent on a continual throughput of new patients through the treatment services, resulting in an average of 6 participants per site per month at the trial conclusion.

### 7.2 Definitive three arm trial

#### 7.2.1 Sampling

The same participant selection method and method of randomisation will be used for the definitive trial as described for the pilot phase, in section 7.1.

#### 7.2.2 Sample size

A clinically important difference in adherence to medication is estimated as an effect size of the order of 0.3. A recent meta-analysis (92) identified a larger effect size for acamprosate versus placebo when converted to drinking outcomes of the order of 0.4, with a number of studies reporting larger effects. In addition a major issue mediating the potential effect of acamprosate relates to adherence with very low rates reported in UK trials. This effect translates to what is considered a clinically important difference in mental health interventions in terms of a numbers needed to treat of 8, in that if any intervention strategy is found to be superior 8 participants would need to be treated to create an additional participant who is abstinent. As with all pragmatic studies final interpretation will be based upon actual effects observed and the integration of economic outcomes, but an effect size of less than 0.3 is unlikely to be clinically important.

To estimate this difference using power of 80%, alpha 0.05 with a 2 sided tested and differential allocation of 2:1:1 requires 524 analysed at the primary end-point, 6 months across the three groups. Allowing for attrition of 30%, less than observed in other trials in similar populations, requires a total sample size at allocation of 748; 374 allocated to SS, and 187 to SS+MM and 187 to SS+MM+CM. In addition to addressing the primary outcome the sample size is sufficient to identify a

clinically important difference effect size of 0.3 in alcohol consumption measures at 6 and 12 months post-randomisation.

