## 1. Summary of research

Design: 3-arm, prospective, pragmatic, randomised controlled, parallel group clinical trial of strategies to enhance adherence to prescribed acamprosate for alcohol dependence. Standard support (SS), SS with adjunctive medication management (SS+MM), SS and MM with adjunctive contingency management (SS+MM+CM). Outcome assessment will be at 6 and 12 months post randomisation.

Setting: Specialist community alcohol treatment services, community pharmacies local to participants and a central telephone support service.

Population: Abstinent alcohol dependent adults, suitable for prescription of acamprosate, willing and able to provide informed consent.

Inclusion criteria: Aged  $\geq 18$ , ICD-10 alcohol dependence, currently abstinent from alcohol, commencing a prescription for acamprosate.

Exclusion criteria: Severe physical/mental illness identified by the treating clinicians, participation in another trial, unable to adequately understand verbal English, current dependence on an illicit substance.

Health technologies: MM provided by pharmacists via a central telephone support service (weekly for 6 weeks and then fortnightly for 6 weeks and then 4-weekly up to 24 weeks). MM plus CM: Small incentives (vouchers) will be provided to reinforce adherence to telephone support, ranging from £2 to £10 for each MM session completed, with a total value of up to £120 for completing all support sessions.

Primary outcome measure: Proportion of prescribed medication taken assessed using Medication Events Monitoring System (MEMS) and cross-verified using pill count and self-report at 6 months post randomisation.

Secondary outcomes: Proportion of prescribed medication taken, estimated by self-report at 12 months post-randomisation. Total alcohol consumed, drinks per drinking day, percent days abstinent in standard drinks (1 standard drink = 8g ethanol) in the previous 90 days derived using the Time Line Follow Back Form 90. Time to first drink, relapse to any drinking and relapse to heavy drinking (8+/6+ UK units for males/females on a single occasion) derived from self-report. Alcohol related problems (Alcohol Problems Questionnaire), alcohol craving (Alcohol Urge Questionnaire) and severity of alcohol dependence. Measured at baseline, 6 and 12 months post-randomisation.

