Process outcome measures: Participants' beliefs about medications (BMQ; measured at baseline and 6 month follow-up), the therapeutic relationship with the care provider (STAR: measured at 6 month follow-up) adverse events (measured at each bi-monthly research visit).

Economic outcome measures: Health related quality of life (EQ-5D-5L) and Adult Service Use Schedule modified for alcohol-misusing populations measured at baseline, 6 and 12 months post-randomisation. Costs associated with the provision of control and trial interventions, including costs associated with delivery, training, management and overheads.

**Primary analysis:** The primary analysis will be conducted using an intention-to-treat approach. As the study involves three arms, the initial step of the primary analysis will use a multiple analysis of covariance, adjusted for stratification factors, to explore for overall effects between the three arms. If evidence of effect is observed a second analysis, using an analysis of covariance, will explore the mean differences in the primary outcome by comparing SS versus SS+MM and SS versus SS+MM+CM. All results will be presented with estimates of precision and associated 95% confidence intervals.

**Economic analysis:** Analysis of the costs and effects of MM with or without CM for alcohol dependence compared to SS. The primary economic perspective will be the health and social care provider perspective. Broader perspectives will be considered in sensitivity analyses (i.e. criminal justice contacts and criminal activity, patient and family costs).

**Sample size:** Differential allocation of the order of 2:1:1 to maximize the utility of resources with twice as many being allocated to the SS group than the intervention groups. A clinically important difference in adherence to medication is estimated as an effect size of the order of 0.3. To estimate this difference using power of 80%, alpha 0.05 with a 2 sided test requires 524 analysed at 6 months post-randomisation across the three groups. Allowing for attrition of 30%, less than observed in other trials in similar populations, requires a total sample size at allocation of 748; 374 allocated to SS, and 187 each to SS+MM and SS+MM+CM. In addition to addressing the primary outcome the sample size is sufficient to identify a clinically important difference effect size of 0.3 for alcohol consumption measures at both 6 and 12 months post randomization.

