## **5. Background and rationale**

Alcohol misuse is a global problem and is the third leading cause of disability in Europe (1). In the UK, there has been a consistent, year on year increase in harm related to alcohol. Alcohol-

related NHS hospital admissions have more than doubled since 2002/03, with an estimated 1,220,300 admissions related to alcohol in 2011/12 (2). Chronic health conditions related to alcohol have increased in prevalence in the UK, including liver cancer, pancreatitis, alcoholic liver-disease and alcohol use disorders (3). Mental health may be negatively affected by the chronic, heavy use of alcohol with increased risk of depression, anxiety, suicidality, psychosis and impairments to memory and other cognitive functions. Alcohol may contribute to social problems such as unemployment, criminality, marital breakdown, and domestic violence (4-7). The physical, mental and social problems associated with alcohol place a considerable burden on the UK economy. The estimated cost to the UK economy is £21 billion annually [18], of which the NHS costs are estimated at £3.5 billion (8).

The prevalence of alcohol dependence in the UK is estimated at 9.3% of men and 3.6% of women (9). The number of people entering specialist alcohol treatment has increased each year between 2008, when the Department of Health began collecting data, and 2012 (10). The number successfully completing treatment has also risen over the same reporting period but the majority of those dependent on alcohol undergo frequent episodes of withdrawal and resumption of drinking, as many as 70% of service users relapse in the first 12 months post treatment (11, 12). Improved treatment for alcohol dependence has been identified as a priority in the UK Government's Alcohol Strategy (8). Providing effective treatment for alcohol dependence to reduce relapse rates and therefore alcohol associated harms will contribute to this objective.

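### The statement that the sample suffices for a 0.3 effect on alcohol consumption at 6 and 12 months is supported only at month 6, and only for measures that every participant has

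*Protocol*

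**What the plan says.** Section 7.2.2 of the Protocol starts from adherence: "A clinically important difference in adherence to medication is estimated as an effect size of the order of 0.3". With 80% power, a two-sided alpha of 0.05 and 2:1:1 allocation, it "requires 524 analysed at the primary end-point, 6 months across the three groups". Allowing 30% attrition brings the number randomised to 748 (374, 187 and 187).

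The same section then extends the result, without further calculation: "In addition to addressing the primary outcome the sample size is sufficient to identify a" difference of 0.3 in alcohol consumption at both follow-ups. The Summary makes the same claim, for a "clinically important difference effect size of 0.3 for alcohol consumption measures at both 6 and 12 months post randomization".

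The Summary lists the consumption measures as "Total alcohol consumed, drinks per drinking day, percent days abstinent in standard drinks", over the previous 90 days. Section 7.1.10.2, which defines the secondary measures, names percentage days abstinent and units per drinking day but not total alcohol consumed. Participants are abstinent at entry (sections 7.1.2 and 7.1.3.1).

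**The concern.** A sample size that only just reaches 80% power for one outcome at one visit is said to suffice for several other outcomes, including some at a later visit. Two features of the design stand against that.

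First, the attrition allowance is tied to month 6. The 12-month contact is a separate, later visit (section 7.1.1), and nothing is set aside for losses between the two.

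Second, units per drinking day is a ratio with drinking days as its denominator. A participant with no drinking day in the recall window has no value, so the number available for this measure falls below 524 as soon as some participants stay abstinent, which is what the treatment aims at.

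What is at stake is how secondary results are read. Readers of an inconclusive drinking result at 12 months, or of one on units per drinking day, would take from the protocol that an effect of 0.3 was well covered. For those results the coverage is lower, by an amount the protocol does not state.

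**Working it through.** **Inputs from the Protocol.** From section 7.2.2: effect 0.3 (SD = 1), power 80%, two-sided alpha 0.05, allocation 2:1:1, 524 analysed at 6 months, 30% attrition, 748 randomised. The protocol gives neither a cumulative loss at 12 months nor a share of participants with a drinking day in the 90-day window. Both are assumed below and shown as ranges.

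**Reproducing the plan's figure.** For one comparison of SS with an intervention arm at 2:1:

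- Intervention arm: n = 1.5 × (1.960 + 0.842)² / 0.3² = 130.8, so 131. SS needs 262. Total 262 + 131 + 131 = 524, as printed.
- 524 / 0.70 = 748.6, against 748 printed. In the other direction, 748 × 0.70 = 523.6.

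**Power formula.** Let N be the total analysed over the three arms. SS has N/2 and an intervention arm N/4, so n₁n₂/(n₁ + n₂) = N/6, and power ≈ Φ(0.3 × √(N/6) − 1.960).

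For N = 524: 0.3 × √87.33 = 2.804, and Φ(0.844) = 80.1%. The noncentral t gives 79.9%. There is no reserve.

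**Month 6, measures every participant has.** Total alcohol consumed is 0 and percent days abstinent is 100 for an abstainer, so all 524 contribute and power is 80%.

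**Month 12, measures every participant has.** N = 748 × (1 − cumulative loss):

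| Assumed cumulative loss | N | 0.3 × √(N/6) | Power |
|---|---|---|---|
| 30% (no loss after month 6) | 524 | 2.80 | 80% |
| 35% | 486 | 2.70 | 77% |
| 40% | 449 | 2.59 | 74% |
| 45% | 411 | 2.48 | 70% |
| 50% | 374 | 2.37 | 66% |

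By the noncentral t, the effect detectable with 80% power is about 0.325 at 40% loss and 0.356 at 50% loss.

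**Units per drinking day at month 6, analysed where defined.** N = 524 × share with a drinking day:

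| Assumed share | N | 0.3 × √(N/6) | Power |
|---|---|---|---|
| 90% | 472 | 2.66 | 76% |
| 80% | 419 | 2.51 | 71% |
| 70% | 367 | 2.35 | 65% |
| 60% | 314 | 2.17 | 58% |

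The noncentral t changes none of these powers by more than 0.4 percentage points. The two reductions multiply: 40% loss with a 70% share leaves 748 × 0.60 × 0.70 = 314, or about 58% power.

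**The case against.** **Covariate adjustment.** Section 7.2.4 adjusts the drinking outcomes for SADQ, site, age and gender, while the figures above are unadjusted. Covariates explaining about 7% of the variance would offset a 35% loss (486/524 = 0.93), and about 14% would offset a 40% loss (449/524 = 0.86). So the exact shortfall is not fixed. But section 7.2.2 claims no such gain, gives no variance explained, and reaches 524 without adjustment.

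**Handling of abstainers.** The protocol leaves the drinking models to a later analysis plan, which might score abstainers as zero on units per drinking day. That restores the number analysed but changes the measure: it would no longer be intensity on drinking days. The unqualified statement remains unsupported for the measure as named.

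**No power level is stated.** The sentence says only that the sample is sufficient. It closes the paragraph that sets 80% power at alpha 0.05, so readers will naturally carry those values over.

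**Stronger readings to avoid.**

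- A reader might infer that power for alcohol consumption is about 65% in general. It is not. That figure needs either units per drinking day with 70% drinking, or about 51% cumulative loss.
- A reader might take the background remark that "as many as 70% of service users relapse in the first 12 months post treatment" to mean that at least 30% will have no value. It does not establish this. It is a general figure over 12 months, relapse is not defined there, and the outcome window is 90 days. The true share could lie on either side of 70%.
- A reader might charge the trial with a biased comparison among drinkers only. The protocol nowhere specifies that analysis.

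**Conclusion.** The statement is correct at month 6 for total alcohol consumed and percent days abstinent, provided the effect is 0.3 SD and 524 are observed. It is unsupported in two places. At 12 months it needs zero loss after month 6; power is about 77% to 66% for assumed cumulative losses of 35% to 50%. For units per drinking day, power is below 80% even at month 6 if the measure is analysed where defined: about 76% to 58% for assumed shares of 90% to 60%.

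All these figures are for an unadjusted, two-sided 0.05 comparison of SS with one intervention arm. The existence of the gap follows from the protocol's own numbers and definitions; its size rests on the assumed losses and shares. These are secondary outcomes, so the fault is an overstated assurance. The primary calculation reproduces and stands.

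**What to change.** In section 7.2.2 and in the Summary:

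- Limit the statement on a 0.3 effect to total alcohol consumed and percent days abstinent at 6 months.
- For 12 months, give an assumed cumulative loss with the resulting power or detectable effect, for example about 0.325 at 40% or 0.356 at 50%.
- Leave units per drinking day out of the statement, or give its power under an explicit assumed share of participants who drink.

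In section 7.1.10.2, name total alcohol consumed over the 90 days, with abstainers counted as zero, as the consumption measure to which the statement applies. The Summary already lists it and the TLFB already supplies it.

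The change is to wording only and needs no extra participants or data. The price is a less favourable power statement for the secondary outcomes.

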### 7.2.3 Data collection

Data will be collected in accordance with the methods detailed in section 7.1.

### 7.2.4 Data analysis

In the main trial the primary outcome measure is percent prescribed medication taken at 24 weeks post-randomisation assessed using a triangulation method. After checking for distributional assumptions and employing necessary transformations, an initial multiple analysis of covariance will be undertaken using a mixed model approach addressing the observed differences between SS versus SS+MM versus SS+MM+CM. If this analysis provides evidence of effect a second analysis of covariance will explore the differences of SS versus SS+MM and SS versus SS+MM+CM. Covariates included in the analysis will include stratification variables, gender and body weight (<60kg or 60+ kg). Mean differences between the groups will be presented with associated 95% confidence intervals. Multiple imputation will be employed to address the nature of missing data and sensitivity analysis will address the influence of missing data on the observed outcome. Secondary analysis will address drinking outcomes at 6 and 12 months using appropriate modelling approaches and these will be adjusted for known confounders; SADQ, site, age and gender. Time to relapse and relapse to heavy drinking will be assessed using survival analysis. Further secondary analyses will explore adherence data at 12 months. We will explore the association between adherence and drinking outcomes using a linear regression adjusted for known confounders and include an adherence\*allocation interaction term. As with most trials the analysis plan will be refined throughout the course of the study and the final analysis plan prepared and agreed by the research team and Trial Steering Committee.

Further analysis will be conducted to identify interactions between variables, including ratings of therapeutic relationship, and fidelity of MM and CM delivery, on clinical and adherence outcomes. The analysis will be governed by an explicit data analysis plan agreed in advance by the Trial Steering Committee.

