the person's concerns about the potential adverse effects of the medication. In chronic health conditions such as asthma, diabetes, cardiac disease and cancer, a greater perception of the benefits of a medication is associated with greater adherence, and greater concern about adverse effects of a medication is associated with poorer adherence (40, 41). The development of effective interventions to improve patients' uncertainties about the necessity for medication and concerns about the potential adverse effects is a priority to enhance adherence in chronic health conditions (23, 41)

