#### 7.1.9 Randomisation

The proposed trial involves differential allocation of the order of 2:1:1 to maximize the utility of resources with twice as many being allocated to the SS group than the intervention groups. Randomisation will be carried out after consent has been gained and the initial baseline assessment has been conducted. A remote randomisation procedure will be used through an online system developed and maintained by Codeface Ltd to generate the treatment allocation, which will be initiated by a trained researcher. It is not possible for participants and the study team to be blind to treatment allocation. Allocation will employ a stratified random permuted block method with stratification by severity of alcohol dependence (SADQ score of  $\leq 30$  or  $>30$ ), site and the prescription of other relapse prevention medication. These variables are known to be related to clinical outcomes and will be collected at preliminary screening.

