BMQ	Beliefs about medication specific to their health and general medication beliefs				
EQ-5D-5L	Health related quality of life				
AD-SUS	Service use				
STAR	Therapeutic relationship with pharmacist delivering MM				
MMAS	Assess self-reported adherence to acamprosate				
MEMS	Percentage medication taken as prescribed				
Pill count	Percentage of pills taken				
Self-reported adherence	Percentage of pills taken Reasons for non-adherence				

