#### *7.1.10.2 Secondary outcome measures*

At baseline assessment participant demographics will be collected as well as a history of use of acamprosate, other relapse prevention medication use, and previous medically assisted

detoxification using a medical history checklist devised specifically for the trial. The substance use section of the Alcohol, Smoking and Substance Involvement Screening Test- Lite (ASSIST-Lite;(13)) will be administered to obtain a history of any substance use.

Severity of dependence will be measured at the initial screening assessment and at 6 and 12 month follow-up using the Severity of Alcohol Dependence Questionnaire (SADQ) (85). The SADQ is a 20-item self-complete questionnaire containing items representing five domains of the alcohol dependence syndrome: (i) physical withdrawal signs (ii) psychological withdrawal signs (iii) withdrawal relief drinking (iv) tolerance (v) reinstatement following a period of abstinence.

Alcohol consumption will be measured using the Time Line Follow Back (TLFB) Form 90 (86), administered at initial screening assessment and at 6 and 12 month follow-up after initiation of acamprosate. Percentage days abstinent, units of alcohol per drinking day (1 UK unit = 8g alcohol), time to first alcoholic drink, relapse to any drinking and relapse to heavy drinking (8+/6+ units for males/females on a single occasion) will be computed.

Participants' beliefs about medications will be assessed using the Beliefs about Medications Questionnaire (BMQ; (87)). The BMQ assesses an individual's beliefs about medication specific to them and their health, as well as their general beliefs about medication. This questionnaire will be administered at initial screening assessment and at 6 month follow-up. The measure will be used to evaluate the impact of MM on beliefs and concerns about medication and the association with adherence to acamprosate.

Participants will be asked to rate their therapeutic relationship with the care provider monitoring their medication adherence at each follow up point using the STAR rating scale (88). Therapeutic relationship (or alliance) has been found to predict clinical outcome across a range of mental disorders (89) including alcohol dependence (90). This will be used as an additional process measure to assess the impact of therapeutic relationship on medication adherence and clinical outcome.

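### The primary adherence model could gain some precision, at almost no cost, by naming the baseline medication-belief scores as covariates, and its covariate set should be stated the same way in both places

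*Protocol*

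**What the plan says.** Section 7.2.4 of the protocol states, for the primary outcome, "Covariates included in the analysis will include stratification variables, gender and body weight", with weight split at 60 kg. The summary in Section 1 describes the first step of the same analysis as "adjusted for stratification factors, to explore for overall effects between the three arms", with no mention of gender or weight. Section 7.1.9 gives the stratifiers as dependence severity (SADQ score up to 30 or above 30), "site and the prescription of other relapse prevention medication".

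Section 5.3 reports that, in several chronic conditions, "a greater perception of the benefits of a medication is associated with greater adherence". For worries about harm it gives the opposite direction: "greater concern about adverse effects of a medication is associated with poorer adherence". The BMQ row of Table 1 (Section 7.1.10) covers "Beliefs about medication specific to their health and general medication beliefs" and is ticked at baseline. Section 7.1.10.2 says of it: "This questionnaire will be administered at initial screening assessment and at 6 month follow-up". Section 7.1.9 places randomisation after the baseline assessment.

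Section 7.2.4 also says that the analysis plan will be refined and agreed with the Trial Steering Committee.

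**The concern.** The primary outcome is adherence over the 24 weeks after randomisation. Table 1 schedules no adherence measure at baseline, so the model cannot adjust for a baseline value of the outcome. Other prognostic baseline variables are then the main way to reduce residual variance.

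The protocol's own theory of why people do or do not take medication rests on necessity and concern beliefs, and every participant is scored on them before allocation. A covariate list that leaves those scores out may therefore give wider intervals than the collected data allow. The two descriptions of the list also differ, which leaves some room for choice in the primary model until they are reconciled.

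The precision of the primary comparison is what is at stake. Its validity is not.

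**Working it through.** **Inputs from Section 7.2.2:** effect size 0.3 (SD units), two-sided alpha 0.05, power 80%, allocation 2:1:1, 524 analysed, 30% attrition, 748 allocated.

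**Assumed input:** r, the correlation of the baseline BMQ scores with adherence after the other covariates (a multiple partial correlation if two scores are used). The protocol gives no figure, so 0.1 to 0.3 is used as a range.

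**Step 1. Reproduce the plan's figure.** For one intervention arm against standard support at 1:2:

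n(SS) = (1 + 2) × (1.960 + 0.842)² / 0.3² = 3 × 7.85 / 0.09 ≈ 261.6, rounded up to 262.

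Each intervention arm is then 131, and 262 + 131 + 131 = 524, an exact match. Allowing for attrition, 524 / 0.70 = 748.6, which agrees with 748 apart from rounding. The calculation contains no covariate term, so the 80% power does not depend on which covariates are used.

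**Step 2. Effect of adding the scores.** Adjustment multiplies the residual variance by (1 − r²), so the standard error is multiplied by √(1 − r²).

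- Unadjusted standard error: √(1/262 + 1/131) = 0.1070.
- Power = Φ(0.3 / (0.1070 × √(1 − r²)) − 1.960).
- Total needed = 2 × the SS arm size, with n(SS) = 261.6 × (1 − r²) rounded up.
- Loss that 748 allocated could absorb = 1 − total needed / 748.

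| Assumed r | √(1 − r²) | Interval narrower by | Power at 0.3 | Total needed | Loss absorbed |
|---|---|---|---|---|---|
| 0 | 1.0000 | 0% | 0.8006 | 524 | 29.9% |
| 0.1 | 0.9950 | 0.5% | 0.8045 | 520 | 30.5% |
| 0.2 | 0.9798 | 2.0% | 0.8163 | 504 | 32.6% |
| 0.3 | 0.9539 | 4.6% | 0.8362 | 478 | 36.1% |

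**Step 3. Cost of the extra terms.** Two added covariates inflate the variance of a pairwise contrast by roughly 2/393 ≈ 0.5%, where 393 = 262 + 131. The table does not subtract this. At r = 0.1 the variance gain is 1%, so about half of it is used up. At 0.2 and 0.3 the gains are 4% and 9%, and the cost is minor.

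**Step 4. Is the covariate legitimate?** The initial BMQ precedes randomisation, so allocation cannot affect it. The 6-month BMQ follows treatment, and Section 7.1.10.2 intends it to show whether medication management changes beliefs. It must therefore stay out of the primary model.

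**The case against.** The strongest case against is that this is optional. Stratifiers plus gender and weight band is a conventional set, and the choice of further prognostic covariates is often left to the analysis plan, which Section 7.2.4 says is still to be refined and agreed.

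Several stronger readings are tempting, and the protocol does not support them:

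- **That the list is closed.** Section 7.2.4 says what the covariates will include. It does not say that nothing else will enter.
- **That the protocol declares beliefs to be predictors of acamprosate adherence.** The associations in Section 5.3 come from conditions such as asthma, diabetes, cardiac disease and cancer. For this trial, Section 6 makes beliefs a secondary hypothesis, as a moderator, and Section 7.1.10.2 plans to study their association with adherence.
- **That age and previous acamprosate use are also wrongly omitted.** Nothing in the protocol ties either to adherence. Section 7.2.4 names age only for the drinking outcomes.
- **That the dichotomised SADQ stratum should be replaced by the score.** Adjusting for the factor as randomised is sound.
- **That the trial is underpowered or biased by the omission.** Step 1 shows that it is not underpowered on this account, and omitting a baseline covariate does not bias a randomised comparison of means.

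The difference between Sections 1 and 7.2.4 may also be no more than a summary abbreviating the full text.

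All of this stands, and it limits the weight of the point. It does not remove it: the protocol does state a list, that list can be improved with data already collected, and the two statements of it should agree.

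**Conclusion.** The point holds as a recommendation to improve efficiency. On the assumed range the likely benefit runs from negligible (r = 0.1) to modest (r = 0.3: interval 4.6% narrower, power 83.6%). These figures rest on an assumed correlation, a linear relation with similar strength across arms, and the analysed numbers being reached. If beliefs turn out to be unrelated to acamprosate adherence, nothing is gained and about 0.5% of variance is lost. The wording mismatch between the summary and Section 7.2.4 is minor but should be removed, because it concerns the primary model.

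**What to change.** Before unblinding, state one covariate set and use it in both the overall three-arm model and the pairwise comparisons:

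- the stratification factors as randomised (site, SADQ stratum, other relapse prevention medication);
- gender;
- weight band;
- the baseline BMQ necessity and concerns scores, entered as continuous variables.

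Specify that only the baseline BMQ is used, never the 6-month score. Impute missing baseline scores without using treatment arm. The continuous SADQ score may be added alongside its stratum; age and previous acamprosate use are optional. Amend the primary-analysis paragraph in Section 1 to match Section 7.2.4.

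This is a change of wording. It needs no new data collection and costs a few degrees of freedom plus a rule for missing baseline scores.
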